During the final closeout visit at the primary care office, patients will be contacted by letter (and follow-up phone call if needed) by a member of the study team and will be scheduled to return to their primary care provider for the following:

- Review of current eye medications
- Review of current systemic medications
- Review of demographics (address & phone number(s))
- Results of A1C reading (from PCP office)
- Blood pressure reading
- Intraocular Pressure reading
- Smoking status
- Completion of Satisfaction Closeout Survey
- Completion of NEIVFQ questionnaire

C.4.b. Specific Roles of Collaboration/Partnerships: The successful implementation of this research project builds upon Wills' current community partnerships from our CDC demonstration project and new collaborations and infrastructure established by the WETD. Our partnerships maximize the capacity of the intervention to reach and identify people with undiagnosed glaucoma, glaucoma suspect, other eye diseases; and visual impairment among high-risk, vulnerable patients they serve. Patients within each organization are racially and ethnically diverse, as described in Facilities. To ensure the broadest reach and ownership of the proposed intervention, our community partners have been invited to collaborate by joining the Advisory Board and engaging in planning, developing, implementing and evaluating the interventions. These partners include the Public Health Management Corporation, Philadelphia Department of Public Health, Health Federation of Philadelphia, and Temple Physicians, Inc. Since each organization has its own detection and referral system for vision and eye care services, we have developed our specific aims and study design with input from our partners and Advisory Board members (Appendix D).

Partners will also assist in remediating organizational, community, and cultural barriers and will provide facilitators and resources to ensure replication of our protocols, results, and outcomes. We believe that the breadth of the governmental, community, non-profit, and university-based partner organizations and the

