The glaucoma specialist will review the results and final diagnosis with each patient. Criteria for glaucoma or glaucoma suspect will be defined as IOP (>21mm Hg), suspicious disks including a cup-to-disk (C:D) ratio greater than 0.5, C:D asymmetry (> 0.2), disk hemorrhage, or a combination of IOP and C:D appearance. Other eye disease diagnoses, such as DR, will be made using standard *AAO Practice Pattern Guidelines*. Assessment measures and study schedule for Visits 1 through 8 are shown in Table 5.

**Table 5: Assessment Measures and Study Schedule** (PCP=Primary care physician, OPHTHO=general ophthalmologist)

Assessment Measures	Eye Detection Exam Visit 1 PCP	Confirm Diagnosis Baseline Visit 2 PCP	Initial Follow-Up Eye Exam Visit 3 OPHTHO	Ongoing Follow-Up Eye Exam Visit 4 OPHTHO	Ongoing Follow-Up Eye Exam Visit 5 OPHTHO	Ongoing Follow-Up Eye Exam Visit 6 OPHTHO	Ongoing Follow-Up Eye Exam Visit 7 OPHTHO	Final Follow-Up Visit 8 or Final Visit PCP & OPHTHO
Medical, family history	✓	✓	✓	✓	✓	✓	✓	✓
Eye fundus photographs	✓							
Complete eye exam		✓	✓	✓	✓	✓	✓	✓

Intraocular pressure**	✓	✓	✓	✓	✓	✓	✓	✓
Central Corneal Thickness*		✓	✓	✓	✓	✓	✓	✓
Visual field test*		✓	✓	✓	✓	✓	✓	✓
Visual acuity (Snellen)*****	✓	✓	✓	✓	✓	✓	✓	✓
Blood pressure (PCP) ***	✓							✓
Hemoglobin A1C (PCP) ***	✓							✓
Body mass index (PCP) ***	✓							✓
Smoking status	✓	✓	✓	✓	✓	✓	✓	✓
NEI-VFQ-25		✓			✓			✓
Satisfaction survey****	✓	✓	✓	✓	✓	✓	✓	✓
Current eye medications								✓
Current systemic meds.								✓
Confirm type of health insurance								✓
Current demographics (address & phone number(s))								✓

\* Testing will be performed at the discretion and according to the follow-up recommendation of the local ophthalmologist

\*\* IOP at Visit 1 & final visit will be measured by iCARE rebound tonometer by study team.

\*\*\* A1C will be captured from the medical record. Blood pressure will be taken at the final visit by a member of the study team.

\*\*\*\* Satisfaction surveys will be administered for Visit 1 and Visit 2 and then 2-4 times a year based on randomization; a study closeout satisfaction survey will be administered at the final visit.

\*\*\*\*\* Visual Acuity (Snellen) will be taken by study team at the final visit.

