**C.6.a. National Eye Institute-Visual Function Questionnaire (NEI-VFQ):** A member of the research team will consent all patients and administer the validated NEI-VFQ-25 questionnaire at Visit 2, Visit 5 and Visit 8 to assess barriers and the influence of their vision impairment on their health-related quality-of-life. The 12 subscales are calculated by adding the relevant items and transforming the scores into a scale from 0 to 100. Higher scores indicate better quality-of-life. The composite score will be calculated as the average of 12 subscale scores. Patient navigators will use these results to assess barriers and refer patients to appropriate professionals, such as a social worker, low vision specialist, psychiatrist, occupational therapist, Medicare/Medicaid insurance advisor, and/or cataract surgeon. All materials will be culturally and linguistically appropriate and translated into other languages as necessary using trained medical interpreters and we will track all process measures.

\*NEIVFQ surveys will be administered in person to all patients at Visit 2. For Visits 5 and 8 questionnaires will be administered over the phone by a patient navigator or social worker.

**C.6.b. Patient Satisfaction Survey:** With assistance from Westat, our partners, and Advisory Board members, we will create a new survey instrument and administer it at the end of each of the study visits. We will ask patients to rate their satisfaction with the exam, its duration, its convenience, the staff, and the likelihood of attending a follow-up eye exam. These surveys will optimize patient engagement and report outcomes that are important to patients and stakeholders.

\*Satisfaction surveys will be administered in person to all patients for Visits 1 and 2. For Visit 5 surveys will be administered over the phone by a patient navigator or social worker for all enrolled patients. For Visits 3, 4, 6, and 7 satisfaction surveys will be administered according to randomization. For Visit 8 (or final visit), a Study Closeout Satisfaction Survey will be administered at the primary care office by a member of the study team.

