**D.1.b. Effectiveness/Efficacy:** We will evaluate the impact of our enhanced intervention on our proposed outcomes, including quality-of-life, and economic efficiency. Determining the effectiveness of our intervention is critically important because patients with undetected glaucoma and other eye diseases can suffer lasting visual impairment that can affect their quality-of-life, economic status, morbidity, and ultimately mortality. New strategies are necessary to improve patient access and utilization of eye care. Our study aims to determine if adherence to follow-up recommendations changes as a result of the enhanced intervention. We will determine the effectiveness of the intervention by examining the effect size associated with our intervention and specified outcomes (adherence to follow-up recommendations and vision-related quality-of-life).

**D.1.c. Adoption:** Our letters of support from Advisory Board members and partner institutions demonstrate a strong commitment and willingness to participate in this research study. We are working closely with primary care offices, health centers, universities, governmental agencies, and community organizations. We expect to notice variations in patient behavior based on the number of resources available to them. These varying settings and intervention modalities are critical to the current and potential impact of our intervention. If differences exist among sites, this is evidence of differential adoption.

**D.1.d. Implementation:** At each setting, implementation refers to the intervention agents' fidelity to all elements of the protocol. This includes consistency of delivery as intended and the time and cost of the intervention. Investigators in coordination with Westat and the project manager will determine the extent to which the intervention was delivered. We will assess implementation by reporting on the percentage of process objectives that were achieved, such as: What proportion of patients received the confirming diagnosis enrolled in the study? How many patients followed up with the general ophthalmologists at the initial 6-month, 1-year, 2-year, and 3-year visits. We will also conduct a cost analysis and report costs of all levels of the intervention, including recruiting patients, reading images, confirming diagnoses, randomization, and 3-year follow-up (Table 7).

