**Table 7: Tracking Measures Using *RE-AIM Framework* Approach**

RE-AIM	Evaluation Question	Tracking Measures	Data Source
Adoption	How were community partners and primary care settings engaged in the study?	# of participating community partners and primary care settings (offices, health centers). Primary care offices' satisfaction with participation.	Contact log  On-site observations On-site interviews

Reach	To what extent are high risk target populations being reached?	Patient characteristics (demographics, insurance status, ocular history, ocular risk factors).	Intake form/EMR
Implementation	How was the program implemented?	Patient navigator, cultural competency training conducted. # of staff at each onsite activity. # of patients who follow up with general ophthalmologists. Time taken per patient and for each eye exam. # of confirmatory diagnosis from fundus photos. # of referrals made based on NEI-VFQ.	Planning log  On-site observations  EMR
Efficacy/ effectiveness	Did the intervention work? (Comparison between intervention and control groups)	# of patients from each group adhering per year. Average percentage of visits attended per year. Clinical measures (visual acuity, IOP, VF). Health related quality-of-life (Visits 2 and 8). Satisfaction with eye services at each visit.	EMR  EMR NEI-VFQ Patient satisfaction survey
Maintenance	To what extent has the program been institutionalized?	Willingness of partners and PCPs to continue with telemedicine and community model.	On-site interviews

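### The mid-study NEI-VFQ-25 is tied to an undated eye exam (Visit 5) with no rule for missed exams, and the final NEI-VFQ-25 has two conflicting modes

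*Combined protocol and SAP*

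**What the plan says.** Section C.6.a says that staff will "administer the validated NEI-VFQ-25 questionnaire at Visit 2, Visit 5 and Visit 8". Visit 2 is in person; for the rest, "For Visits 5 and 8 questionnaires will be administered over the phone by a patient navigator or social worker". The Table 5 column for the middle assessment reads "Ongoing Follow-Up Eye Exam Visit 5 OPHTHO", with no month or window attached.

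For the end of the study, section C.4.a describes a closeout at the primary care office. The study team writes to patients, telephoning where necessary, and each patient "will be scheduled to return to their primary care provider for the following". One item on the list given there is "Completion of NEIVFQ questionnaire".

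Table 7 gives the time points for comparing the groups as "Health related quality-of-life (Visits 2 and 8"; Visit 5 is not among them. Section D.1.b says effectiveness will be judged on the "specified outcomes (adherence to follow-up recommendations and vision-related quality-of-life". Section E.2.e tests change in the NEI-VFQ by the treatment-by-time term of a mixed model with continuous time, adjusted for age and diagnosis. Section E.2.g relies on missing at random for continuous outcomes and does not impute.

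**The concern.** A repeated quality-of-life measure should be taken at times that do not depend on the patient's disease course or on the behaviour the intervention is meant to change. Visit 5 is an eye exam. Eye exams are spaced by severity and control of disease, and attendance from Visit 4 onward is the Aim 2 primary outcome (E.2.b). A questionnaire attached to that exam has no common date. It may also have no date at all for someone who stops attending.

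At stake is the treatment-by-time comparison for one of the two outcomes named in D.1.b. If the middle assessment came mainly from attenders, and more often in one arm, the missing-at-random assumption would carry more weight than the plan acknowledges. The mode conflict at the final visit is a separate matter: sites could follow different rules, and the mode would then vary between patients for no planned reason.

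**Working it through.** The documents give no sample size, power or expected missing-data rate for the NEI-VFQ-25, so there is no plan figure to reproduce. The check has three parts.

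**1. When Visit 5 falls.** Section C.9 puts Visit 3 within 4 weeks of Visit 2, taken here as month 1. Tables 6 and 9 give recommended intervals of 1-2, 3-6, 6 or 12 months. Visit 5 is the third eye exam, two intervals after Visit 3. With every exam attended on time and the interval unchanged, month of Visit 5 = 1 + 2 × interval:

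- 1-2 months: 1 + 2×1 = 3 to 1 + 2×2 = 5
- 3-6 months: 1 + 2×3 = 7 to 1 + 2×6 = 13
- 6 months: 1 + 2×6 = 13
- 12 months: 1 + 2×12 = 25

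The spread is 25 − 3 = 22 months before any exam is missed. In Table 6 the shortest interval belongs to patients with progressing damage and the longest to stable, controlled patients, so the date follows severity. Section D.1.d mentions 6-month and yearly visits but does not map them to visit numbers.

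**2. What follows if the call depends on an attended exam.** This is an illustration under a condition the documents do not state. Take patients on a 12-month interval, for whom one visit a year counts as adherent (Table 9), so that Table 10's annual adherence can serve as attendance per exam. Assume Visit 3 is attended and attendance is independent from exam to exam. The share reaching Visit 5 on time is then p²:

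- 40% vs 60%: 0.40² = 16% vs 0.60² = 36%
- 35% vs 55% (lowest row of Table 10): 12% vs 30%
- 60% vs 80% (highest row): 36% vs 64%

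If instead the same people attend every time, the shares equal the attendance rates (40% vs 60%). If every enrolled patient is phoned regardless of attendance, this difference does not arise.

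**3. The final questionnaire, side by side.**

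- C.4.a: completed as part of a return visit to the primary care office.
- C.6.a: given by phone at Visit 8.
- C.6.b: the closeout satisfaction survey is given at the primary care office, which fits C.4.a and leaves the phone call for the NEI-VFQ-25 unexplained.
- Time points: Table 5 and C.6.a list Visits 2, 5 and 8; Table 7 lists Visits 2 and 8.

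These cannot all be followed as written.

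**The case against.** The strongest objection is that no sentence makes the Visit 5 call conditional on an attended exam. Study staff place the call, and in C.6.b the companion satisfaction survey at Visit 5 goes by phone to everyone enrolled. A reader might infer that quality-of-life data will be missing according to attendance, differently by arm, as a built-in feature of the design. The documents do not support that. Nor do they exclude it: C.6.a refers to all patients only at Visit 2, C.4.a and Table 8 describe the numbered follow-up visits as attended appointments, and no date is given for calling someone who has missed exams. The objection therefore removes the certainty but leaves the gap.

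Three further objections stand in part:

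- **Timing.** Continuous time in the mixed model accommodates uneven dates, provided actual dates are used. The plan does not say so, and does not say how the first-order autoregressive structure treats unequal spacing.
- **Missingness.** Not imputing is normal for a likelihood-based model. Dropout explained by arm, age, diagnosis or earlier scores is covered; only dropout related to unobserved quality of life is a problem, and the documents give no evidence of its size.
- **Mode.** A reader might infer that moving from an in-person baseline to the phone biases the comparison of arms. If both arms change mode alike, the shift largely cancels from the treatment-by-time term. It would still blur change within an arm.

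The mode conflict also does not show that final data will be missing by eye-exam attendance. The closeout is arranged by the study team and is not conditional on earlier eye exams.

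**Conclusion.** Two points are established from the text. The mid-study NEI-VFQ-25 has no calendar definition and no rule for missed exams, and its planned date ranges from about month 3 to month 25, assuming Visit 3 at month 1, full attendance and unchanged intervals. The final NEI-VFQ-25 has two incompatible modes, and Table 7 disagrees with Table 5 and C.6.a on the time points.

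Dependence of data availability on attendance, and hence a difference between arms, is a possibility the plan leaves open. The 16% versus 36% measures that possibility under stated assumptions and is not a forecast. The affected analysis is the secondary one in E.2.e; the primary adherence test is not. The point is worth correcting because the correction is cheap.

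**What to change.** In C.6.a and Table 5, replace Visit 5 for the NEI-VFQ-25 with a fixed time after randomisation, for example 12 months with a stated window, by phone for every randomised patient whether or not an eye exam took place. Month 12 is only an example; what matters is a common date independent of attendance. State in E.2.e that actual assessment dates are used in the mixed model.

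Reconcile C.4.a and C.6.a to one primary mode for the final NEI-VFQ-25, the same in both arms, and record the mode actually used. The choice is a trade-off: in person matches the baseline mode but depends on patients returning to the office, while phone avoids that but changes mode from baseline. Align Table 7 with the chosen time points.

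The cost is protocol wording. Planned contacts per patient do not rise; the downside is a few more calls to patients who would not otherwise have reached Visit 5.

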Usual care patients will be mailed the survey with a self-addressed stamped envelope to return the instrument to Wills Eye Hospital upon completion. Intervention group patients will be called and the survey will be conducted over the phone by a patient navigator or social worker. Satisfaction surveys will be administered 2 to 4 times a year within a 4 week window of their follow-up visit.

[figure not shown]

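### At Visits 3, 4, 6 and 7 the satisfaction survey is mailed to usual care but phoned to the intervention arm, yet Table 7 plans a between-group comparison at each visit

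*Combined protocol and SAP*

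**What the plan says.** Section C.6.b sets the survey mode visit by visit. At Visits 1 and 2 every patient is surveyed in person. After that the plan splits: "For Visits 3, 4, 6, and 7 satisfaction surveys will be administered according to randomization". The text that follows explains the split. In usual care, "Usual care patients will be mailed the survey with a self-addressed stamped envelope to return the instrument to Wills Eye Hospital upon completion". In the enhanced arm, "Intervention group patients will be called and the survey will be conducted over the phone by a patient navigator or social worker". The timing is given as "Satisfaction surveys will be administered 2 to 4 times a year within a 4 week window of their follow-up visit".

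Two later points use one mode in both arms. The first is Visit 5: "For Visit 5 surveys will be administered over the phone by a patient navigator or social worker for all enrolled patients". The second is Visit 8 or the final visit, where "a Study Closeout Satisfaction Survey will be administered at the primary care office by a member of the study team". Section C.4.a describes how people are brought in for that closeout visit, with no difference by arm: "patients will be contacted by letter (and follow-up phone call if needed) by a member of the study team".

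The use of the data is described elsewhere. The efficacy/effectiveness row of Table 7 asks whether the intervention worked, labels this a comparison of the two groups, and includes satisfaction at each visit among its measures. E.1.d states the hypothesis that the intervention group will be more satisfied, and C.8.a says that navigators and a social worker will improve satisfaction. None of the three names the visits at which the arms may fairly be compared. E.2 does not mention satisfaction.

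**The concern.** A satisfaction rating can depend on how it is obtained. A form completed alone and posted back differs from an interview by voice, and the two can have different response rates. Here the interviewer also matters: C.4.a defines the enhanced intervention as the use of patient navigators and a social worker, and people in those roles collect the intervention arm's ratings. One of the rated items in C.6.b is the staff.

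If the comparison is made at each visit, as Table 7 indicates, the trial could report a satisfaction benefit (or a lack of one) at Visits 3, 4, 6 and 7 that its own data collection does not allow it to attribute to the intervention. What is at stake is the credibility of a patient-reported supporting outcome, not the adherence result.

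**Working it through.** No arithmetic applies. The plan gives no sample size, power, effect size, return rate or test for satisfaction, so there is no figure to reproduce. The check is to set the survey rules beside the planned use.

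**Step 1. Mode by visit and arm (C.6.b).**

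| Visit | Usual care | Enhanced intervention | Same mode? |
|---|---|---|---|
| 1, 2 | In person | In person | Yes, but normally before randomization |
| 3, 4 | Mailed form | Phone, navigator or social worker | No |
| 5 | Phone, navigator or social worker | Phone, navigator or social worker | Yes |
| 6, 7 | Mailed form | Phone, navigator or social worker | No |
| 8 or final | Primary care office, study team | Primary care office, study team | Yes |

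The mail and phone sentences do not repeat the visit numbers. They directly follow the statement that Visits 3, 4, 6 and 7 go by randomization, and every other visit has its own stated mode, so this reading is secure.

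**Step 2. Count.** There are six follow-up visits (3 to 8). Mode is fixed by arm at four (3, 4, 6, 7) and common at two (5, 8).

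**Step 3. What a difference at those four visits would contain.** At each of them a patient is phoned if and only if assigned to the intervention. The indicator for arm and the indicator for mode are then the same variable, and:

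observed difference = intervention effect + mode effect + interviewer effect + difference due to unequal return

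Data from those visits yield the sum only. Adding a mode term to a model for those visits would not help, because it would be collinear with arm.

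**Step 4. Does any other section resolve it?**
- Table 7 asks for the comparison at each visit, without exception.
- C.8.a and E.1.d state the expected direction without restricting it to same-mode visits.
- E.2.e names intraocular pressure, visual acuity and the NEI-VFQ, but not satisfaction.
- E.2.g covers withdrawal, death and loss of contact for adherence. It has no rule for a survey form that is not returned.

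Nothing resolves it.

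**Step 5. Reach.** E.2.g takes the primary outcome from medical records, so survey mode has no path into the adherence analysis.

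**The case against.** The best defence is that Table 7 is a list of tracking measures under an evaluation framework, not an analysis specification. No test, time point or alpha is attached to satisfaction, and E.2 omits it. Two same-mode points already exist after randomization, so a sound comparison is available. Much of what is rated is the local provider's exam, which may limit any interviewer effect. All of this stands, and it keeps the point modest. It does not remove it: the Table 7 row is labelled a group comparison, E.1.d gives a directional hypothesis, and no text directs the comparison to the two suitable visits.

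A modeller might add that a longitudinal model could estimate the mode effect from the switch to phone in usual care at Visit 5. That works only if the true intervention effect is assumed constant over visits. The plan specifies no such model, and the separation would still come from the same-mode visits.

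Three stronger readings are tempting, and the documents do not support them:
- *The bias favours the intervention, and its size can be estimated.* Courtesy toward a navigator would push that way, but unreturned mail could push either way. Any false-positive rate would need an assumed mode shift, return rate, attendance rate and baseline satisfaction, none of which the plan gives for this survey.
- *Visit 5 respondents are selected by attendance.* The timing sentence ties surveys to a follow-up visit, but the Visit 5 sentence covers all enrolled patients. Selection is possible but not established.
- *Table 5 contradicts C.6.b on Visit 5.* Its footnote says "Satisfaction surveys will be administered for Visit 1 and Visit 2 and then 2-4 times a year based on randomization" with no Visit 5 exception. C.6.b gives the specific rule, so this is at most an editorial mismatch.

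**Conclusion.** The point holds, with limited reach. At Visits 3, 4, 6 and 7, four of the six follow-up visits, survey mode and interviewer coincide completely with arm, and a between-group satisfaction comparison there cannot be attributed to the intervention. The plan's wording nevertheless invites that comparison. This follows from the text alone and rests on no numerical assumption.

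The size and direction of any bias cannot be derived from the documents. Satisfaction is a supporting outcome, and the adherence conclusion is unaffected. A change is worth making because it is cheap and because E.1.d commits the trial to a directional claim. Nor does the problem spoil satisfaction altogether: Visit 5 and the closeout survey are free of the mode difference, although each has its own weakness.

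**What to change.** Add to E.1.d, in substance: *The between-group satisfaction comparison will use only the visits after randomization at which both arms are surveyed in the same way, namely Visit 5 and the closeout survey. Results from Visits 3, 4, 6 and 7 will be described by arm, with no between-arm inference.* Change the satisfaction line in Table 7 to match.

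Two reporting additions go with this:
- At every visit, report the numbers surveyed and responding in each arm. This matters at closeout too, because that survey depends on patients returning to the primary care office.
- Record who gave each survey. Visit 5 interviewers are navigators or social workers, and C.8 says study staff are trained as navigators, so the closeout interviewer may be one as well.

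While editing, the Table 5 footnote can be aligned with the Visit 5 rule in C.6.b.

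The cost is a few lines of text and one data field, with no new visits, staff or patients. The downsides are that fewer surveys feed the comparison, and that the closeout survey is separately named and may not carry the same items as the visit surveys.
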